### 11.4 DEATHS

Information for all subjects who died within 30 days of the last dose of treatment, including the cohort, date of death, last oral treprostinil dose date, last oral treprostinil dose (mg), cause of death, PT, and relationship to oral treprostinil will be listed. The number and percentage of subjects who died will be summarized by cohort along with the causes of death reported.

#### 11.5 DISEASE-RELATED EVENTS

Disease-related events that appeared or worsened (with clinical significance) during the study will be captured, including abdominal pain, anorexia, ascites, cool extremities, cor pulmonale, cough, cyanosis, hemoptysis, heart failure (or exacerbation of), hypoxia, loss of consciousness, nausea, pallor, palpitations/cardiac arrhythmia, paroxysmal nocturnal dyspnea, exacerbation of pulmonary hypertension, tachycardia, weight loss/gain, vasovagal reaction, and vomiting. The assessment of each of these disease-related events will be listed by cohort and subject. The number and percentage of subjects noting the onset or worsening of each of these events will be summarized by cohort.

### 11.6 VITAL SIGNS

Vitals signs (blood pressure [systolic and diastolic], heart rate, respiratory rate, and temperature [°C]) along with weight measurements will be captured during all study visits, including days of the inpatient hospital stay for Cohort 1. Height and body mass index were recorded at Screening only.

All vital sign assessments, including weight and height, will be listed by cohort, subject, and scheduled time point in chronological order using the units captured on the eCRF. Weight and height will be converted to a single unit for summarization; specifically, weight will be converted to kg and height will be converted to cm. The summary of vital signs will include descriptive statistics of the applicable parameters at each time point by cohort, including changes from Baseline.

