### 8 GENERAL CONSIDERATIONS FOR DATA ANALYSES

All of the data included in the final locked database will be listed. In general, listings will be sorted by cohort, subject, and scheduled assessment (if applicable). Listings will include assessment date, assessment time (if available), and study day. For data collected on a fixed schedule, the assessment identifier will also be included on the listing.

In general, the data will be summarized by scheduled assessment (if applicable). For continuous variables, the summary statistics will include number of subjects, mean, standard deviation (SD), median, minimum, and maximum.

Minimums and maximums will be expressed using the level of precision in which the variable was collected. All other statistics will be rounded, using an additional decimal point. For discrete variables, summaries will include the frequency and percentage in each category. Percentages will be rounded to 1 decimal point. Whenever practical, categories of discrete variables will be ordered and labeled as they appear in the eCRF, and all categories represented on the eCRF will be included in summaries, even when they do not apply to any subjects in the study.

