### 10.6 PANAMA FUNCTIONAL CLASS

The Panama Functional Class is collected at Screening, Baseline, Week 3, Week 6, Week 12, and Week 24 or premature termination. The listing will include the date of assessment and the functional class (I, II, IIIa, IIIb, and IV). The summary table will use descriptive statistics to present the number (percentage) of subjects within each functional class at each time point starting from Baseline. Shifts from Baseline will also be summarized utilizing the categories improved, no change, and deteriorated at each post-Baseline visit separately by cohort.

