14.3.1.3	Summary of Treatment-emergent Adverse Events by System Organ Class and Preferred Term	_ae_soc
14.3.1.4	Summary of Treatment-emergent Adverse Events by Preferred Term	_ae_pt
14.3.1.5	Summary of Attributable Treatment-emergent Adverse Events by System Organ Class and Preferred Term	_relae_soc
14.3.1.6	Summary of Attributable Treatment-emergent Adverse Events by Preferred Term	_relae_pt
14.3.1.7	Summary of Treatment-emergent Adverse Events by Preferred Term and Severity	_ae_sev
14.3.1.8	Summary of Treatment-emergent Adverse Events Leading to Oral Treprostinil Discontinuation by Preferred Term	_ae_discon
14.3.1.9	Summary of Serious Treatment-emergent Adverse Events by System Organ Class and Preferred Term	_sae_soc
14.3.1.10	Summary of Serious Treatment-emergent Adverse Events by Preferred Term	_sae_pt
14.3.1.11	Summary of Serious Attributable Treatment-emergent Adverse Events by System Organ Class and Preferred Term	_relsae_soc
14.3.1.12	Summary of Serious Attributable Treatment-emergent Adverse Events by Preferred Term	_relsae_pt
14.3.1.13	Summary of Disease-related Events	_dre
14.3.2.1	Listing of Deaths	_death
14.3.2.2	Summary of Deaths	_ldeath
14.3.2.3	Listing of Serious Adverse Events	_lsae
14.3.4.1	Summary of Vital Signs During Week 0 for Cohort 1	_vs
14.3.4.2	Summary of Vital Signs	_vs
14.3.4.3.1	Summary of Hematology Laboratory Data	_lb
14.3.4.3.2	Summary of Hematology Shifts	_lbshft
14.3.4.4.1	Summary of Clinical Chemistry Laboratory Data	_lb
14.3.4.4.2	Summary of Clinical Chemistry Shifts	_lbshft
14.3.4.5	Summary of 12-Lead Electrocardiogram Parameters	_ecg

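### Weight in children aged 7 to 17 is summarised only in kg, so an average gain over 24 weeks does not show whether they gained as expected for age and sex

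*SAP*

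**What the plan says.** Protocol 4.1 admits children aged 7 to 17. The synopsis gives a 24-week uncontrolled study, and Protocol 3.3.2.2 takes weight with the vital signs at every visit. SAP 11.6 converts weight to kg for summary and states: "The summary of vital signs will include descriptive statistics of the applicable parameters at each time point by cohort, including changes from Baseline". SAP 8 defines those statistics: "For continuous variables, the summary statistics will include number of subjects, mean, standard deviation (SD), median, minimum, and maximum". Nothing in SAP 11.6 or the table list refers weight to age or sex.

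Other relevant provisions:

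- Individual data: "All vital sign assessments, including weight and height, will be listed by cohort, subject, and scheduled time point in chronological order".
- Height: "Height and body mass index were recorded at Screening only".
- Cohort 1 inpatient days have a separate table, 14.3.4.1, titled "Summary of Vital Signs During Week 0 for Cohort 1". The remaining visits are in Table 14.3.4.2.
- SAP 11.5 counts clinically significant disease-related events. Its list ends with "tachycardia, weight loss/gain, vasovagal reaction, and vomiting". Protocol Table 9-1 gives weight loss and weight gain as two separate terms.
- SAP 8 also says that "all categories represented on the eCRF will be included in summaries".
- Panama class mentions growth in some of its definitions (Protocol 15.2), and SAP 10.6 says: "Shifts from Baseline will also be summarized utilizing the categories improved, no change, and deteriorated at each post-Baseline visit separately by cohort".

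**The concern.** Most children in this age range are growing. Without a control group, the change in kg is the sum of expected growth and any effect of drug or disease, and the planned statistics cannot separate the two. A reader who sees a positive mean may take it as reassurance when it could equally be a shortfall.

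The question is reasonable to ask here because safety and tolerability are the primary objective and Protocol 1.2.4 names diarrhea and nausea among the frequent drug effects. What is at stake is how one safety table can be interpreted. No endpoint, power or error rate is involved.

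**Working it through.** The documents give no figure on expected weight gain, so there is nothing to reproduce. The calculation below is an illustration.

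**Inputs from the documents.** 24 weeks; 10 to 15 subjects per cohort (SAP 6); n, mean, SD, median, minimum and maximum (SAP 8).

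**Assumptions, not in the documents.** Expected gain of 0 to 6 kg per year; between-child SD of the 24-week change, s, of 0.5 to 1.5 kg, normally distributed.

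**Step 1: expected growth over the study.** Gain = annual rate × 24/52. Rates of 0, 1, 2, 4 and 6 kg per year give 0, 0.46, 0.92, 1.85 and 2.77 kg.

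**Step 2: two cohorts of 15 with the same mean.**
- Cohort A: 5 children gain nothing on average and 10 grow at 4 kg per year. Mean = 10 × 1.846/15 = 1.23 kg. The average shortfall against 4 kg per year is 5 × 1.846/15 = 0.62 kg.
- Cohort B: all 15 grow at one rate, with no shortfall. The rate giving the same mean is 1.231 × 52/24 = 2.67 kg per year.

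**Step 3: do the other planned statistics separate them?** Expected values from 200,000 simulated cohorts:

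| s (kg) | SD, A vs B | Minimum, A vs B | Median, A vs B | Sampling SD of A's SD |
|---|---|---|---|---|
| 0.5 | 1.02 vs 0.49 | −0.58 vs 0.36 | 1.52 vs 1.23 | 0.13 |
| 1.0 | 1.33 vs 0.98 | −1.18 vs −0.51 | 1.32 vs 1.23 | 0.23 |
| 1.5 | 1.72 vs 1.47 | −1.86 vs −1.37 | 1.27 vs 1.23 | 0.32 |

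At s = 0.5 the SD and minimum separate the cohorts. At s = 1.5 the SDs differ by 0.25, less than the sampling SD of 0.32, so a single cohort could not be classified. At s = 1.0 the difference of 0.35 is about one and a half sampling SDs.

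**Step 4: a shortfall shared by all children.** If every child falls short by the same amount, the SD is unaffected. A mean gain of 0.5 kg means a shortfall of 0.5, 1.0 or 2.0 kg if the expected gain was 1.0, 1.5 or 2.5 kg. Only an age and sex reference distinguishes these.

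**Step 5: where the point does not apply.** With expected growth near zero, as for the oldest subjects, kg change is itself the deviation from expectation.

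**Step 6: how precise would an age-referenced mean be?** As a rough guide, treat the z-score change as a kg shortfall at a common age. The 95% half-width at n = 15 is 2.145 × SD/√15 = 0.554 × SD. With Cohort A's SDs this is 0.57, 0.74 and 0.95 kg, against a mean shortfall of 0.62 kg. The adjusted mean is therefore imprecise at s = 1.0 and 1.5.

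**The case against.** The strongest reply is that relevant weight loss is already covered. SAP 11.5 counts clinically significant weight events, and separately anorexia, nausea and vomiting. SAP 11.3 tabulates adverse events by preferred term. Clinically significant findings become adverse events under Protocol 3.3.2.1. Every weight is listed, and with 40 subjects a reader can go through them. The minimum change shows the largest loss. SAP 11.6 also follows Protocol 10.3.3, and no other vital sign gets an age-standardised score. All of this stands, so a reader should not infer that the plan would hide weight loss. But none of these routes gives an age-referenced measure: the event routes depend on judgement, and Panama class mentions growth only as part of a composite.

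The second reply is that a z-score mean is too imprecise at this sample size. Step 6 supports that. The case for it is that it removes a known growth component, not that it gains power.

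Two further changes may look attractive but are not supported.

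- **A count of children losing at least 5% of weight.** The documents contain no such threshold, and it performs poorly. In Cohort A at a common weight of 35 kg the cut is 1.75 kg. The probability that nobody is flagged is Φ(1.75/s)⁵ × Φ((1.75 + 1.846)/s)¹⁰, which is above 99%, 81% and 48% for s = 0.5, 1.0 and 1.5.
- **Calling the combined weight item in SAP 11.5 an error.** The label may be shorthand. The same list joins palpitations and cardiac arrhythmia, which Protocol Table 9-1 also lists separately. The eCRF is not available, and SAP 8 requires its categories to be shown. It is a question for the sponsor.

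**Conclusion.** The point holds as a minor gap in safety reporting. In growing children followed for 24 weeks without a control group, kg and kg change do not show whether weight gain was as expected for age and sex. In the illustration, a mean of 1.23 kg fits both an average shortfall of 0.62 kg and no shortfall at all. How far the other statistics reveal a shortfall confined to some children depends on the between-child spread, which the documents do not give. The growth rates are likewise assumed. The point lapses where expected growth is near zero. It does not show that weight gain will be impaired, and it has no bearing on the primary endpoint.

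**What to change.** In SAP 11.6 and Table 14.3.4.2, add weight-for-age z-score and its change from Baseline at Weeks 12 and 24, by cohort, beside the kg figures. Compute it from sex, exact age at the visit and one growth reference named in the SAP. Leave the inpatient Table 14.3.4.1 as it is. Add a footnote that the score is descriptive, is imprecise with 10 to 15 children per cohort, also reflects fluid status and stature, and does not assign cause. A height-adjusted score is not possible after Screening, because height is not measured again.

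For SAP 11.5 and Table 14.3.1.13, ask the sponsor to confirm that weight loss and weight gain are reported with their direction.

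The cost is a few lines of SAP text, a few table rows and minor programming. Date of birth, gender, visit date and weight are already collected, so subjects bear no extra burden. The limitation is that cause stays unresolved: Protocol 4.3.1 does not capture dose changes of concomitant medications such as diuretics in the eCRF, so a fluid effect cannot be separated out.

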### 11.7 CLINICAL LABORATORY EVALUATIONS

## 11.7.1 Hematology

Hematology laboratory evaluations were performed at Screening, Baseline, Week 12, and Week 24 or premature termination. Hematology data, including hemoglobin (g/L), hematocrit (fraction), red blood cell count (x  $10^{12}$ /L), red blood cell morphology (as required), white blood cell count (x  $10^{9}$ /L), and platelet count (absolute) (x  $10^{9}$ /L) will be listed by cohort and time point, including collection date/time, reference range, and high/low flags.

The summary of hematology laboratory parameters will include descriptive statistics of all parameters at each time point (except Screening), including changes from Baseline by cohort. Additionally a shift table will be generated displaying the number (percent) of subjects with low, normal, and high values at baseline and each post-baseline visit.

Mean values of red blood cell count, hemoglobin, hematocrit, platelet count (absolute), and white blood cell count will be plotted across time starting at Baseline, using a different plotting symbol for each cohort. The time points plotted will be denoted as Baseline, Week 12, and Week 24. For plotting purposes, to prevent outlying values from skewing the majority of the data, the maximum y-axis value will follow the rule of 1.5 x IQR above the third quartile, calculated separately for each lab parameter. All values falling outside of the 1.5 x IQR limit will not be plotted. A footnote denoting this methodology will be added to each plot.

## 11.7.2 Clinical Chemistry

Clinical chemistry laboratory evaluations were performed at Screening, Baseline, Week 12, and Week 24 or premature termination. Clinical chemistry data, including sodium (mmol/L), potassium (mmol/L), bicarbonate (x 10^9/L), chloride (mmol/L), total bilirubin (umol/L), alkaline phosphatase (IU/L), alanine aminotransferase (ALT) (IU/L), aspartate aminotransferase (AST) (IU/L), blood urea nitrogen (BUN) (mmol/L), creatinine (umol/L), calcium (mmol/L), and albumin (g/L) will be listed by cohort and time point, including the collection date/time, reference range, and high/low flags.

The summary of clinical chemistry laboratory parameters will include descriptive statistics of all parameters at each time point (except Screening), including changes from Baseline by cohort. Additionally a shift table will be generated displaying the number (percent) of subjects with low, normal, and high values at baseline and each post-baseline visit.

Mean values of sodium, potassium, chloride, bicarbonate, calcium, albumin, total bilirubin, alkaline phosphatase, ALT, AST, BUN, and creatinine will be plotted across time starting at Baseline, using a different plotting symbol for each cohort. The time points plotted will be denoted as Baseline, Week 12, and Week 24. For plotting purposes, to prevent outlying values from skewing the majority of the data, the maximum y-axis value will follow the rule of 1.5 x IQR above the 3rd quartile, calculated separately for each lab parameter. All outlying values falling outside of the 1.5 x IQR limit will not be plotted. A footnote denoting this methodology will be added to each plot.

#### 11.8 OTHER SAFETY MEASURES

## 11.8.1 Electrocardiogram

The ECG assessments will be completed at Baseline and Week 24 or premature termination. The ECG parameters collected will include heart rate, PR interval, QT interval, QRS duration, ECG results (normal/abnormal), and any abnormalities, including assessment of clinical significance and change from Baseline. The listing will include date/time of assessment as well as all parameters measured for each assessment time point by cohort and subject. All 12-lead ECG parameters will be summarized descriptively at each assessment time point by cohort.

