3.3.2.2 Vital Signs

Vital signs will be assessed during all study visits, including every day of the inpatient hospital stay (Cohort 1 subjects only). Vital signs measured will include blood pressure (BP, systolic and diastolic), HR, respiratory rate (RR), temperature (°C), and weight. Vital signs must be assessed following at least five minutes of rest (sitting) to ensure accurate measurement. No other measurements or procedures should be performed during this five-minute period. Vital signs will be collected prior to or after at least 30 minutes following the 6MWT. Vital signs should also be assessed in the case of abnormal clinical signs and symptoms. Height will be recorded at Screening.

3.3.2.3 12-Lead ECG

A 12-lead ECG will be recorded after at least five minutes rest in the semi-recumbent position at Baseline and repeated at Week 24/Premature Termination. Recordings should include lead II as a rhythm strip and contain at least five QRS complexes. The ECG parameters (after at least five minutes rest) include HR, PR interval, QT interval, QRS duration, and any clinically significant abnormalities.

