10.3.3 Safety Analyses

All subjects who receive oral treprostinil (study drug) will be included in the safety population. Statistical summaries of safety data will be descriptive and exploratory in nature,

focusing on the incidence of adverse experiences. The safety data collected in this study will be presented in listings and summary tables.

Treatment-emergent changes in vital signs, ECG recordings, incidence of treatment-emergent AEs, and treatment-emergent changes in clinical laboratory parameters (i.e., hematology, clinical chemistry, and urinalysis) and physical examination will be evaluated.

All AEs will be coded according to the Medical Dictionary for Regulatory Activities (MedDRA) dictionary. The incidence of AEs within each cohort will be presented in summary tables overall and by system organ class and preferred term.

Vital sign and clinical laboratory data collected prior to dosing will serve as Baseline values for evaluation of data collected during the treatment period. Summary statistics will be calculated for measured values at each time point assessed, as well as change from baseline values within each cohort.

No inferential statistical analyses are planned for safety data.

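### The SAP summarises QT without rate correction and plans no numeric change from Baseline for ECG intervals, so a heart-rate change cannot be told from a repolarisation change

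*SAP*

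**What the plan says.** Protocol 3.3.2.3 (12-Lead ECG) says the parameters "include HR, PR interval, QT interval, QRS duration, and any clinically significant abnormalities". SAP 11.8.1 repeats the four numeric items ("The ECG parameters collected will include heart rate, PR interval, QT interval, QRS duration") and adds an overall normal/abnormal result and a description of abnormalities. On timing, "The ECG assessments will be completed at Baseline and Week 24 or premature termination", so each subject has one scheduled ECG before treatment and one after.

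The planned analysis is one sentence: "All 12-lead ECG parameters will be summarized descriptively at each assessment time point by cohort". The list of tables in SAP 13.1 has a single ECG entry, "Summary of 12-Lead Electrocardiogram Parameters" (Table 14.3.4.5). Neither document mentions QTc, a correction formula or the RR interval, and QTc is not among the SAP abbreviations.

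Protocol 10.3.3 says what will be evaluated for safety, beginning "Treatment-emergent changes in vital signs, ECG recordings, incidence of treatment-emergent AEs". It also says "No inferential statistical analyses are planned for safety data".

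**The concern.** There are two linked gaps.

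First, QT depends on heart rate. If heart rate differs between the Baseline and Week 24 ECGs, raw QT moves even when repolarisation has not changed, and a real repolarisation change can be hidden or exaggerated. There is no control group against which to offset a drift in rate, and there is only one scheduled post-baseline recording.

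Second, the protocol aims to evaluate treatment-emergent ECG change, but the SAP plans only values at each visit. SAP 11.6, 11.7.1 and 11.7.2 plan changes from Baseline for vital signs, hematology and chemistry; 11.8.1 does not do so for the ECG intervals. The mention of change from Baseline in 11.8.1 belongs to the list of items collected, next to the clinical-significance assessment of abnormalities. The sentence in Protocol 10.3.3 on change-from-baseline summaries follows one that names vital signs and laboratory data, and does not name ECG.

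At stake is whether the ECG table can say anything about repolarisation in children newly given, or moved to, oral treprostinil. The primary endpoint is not affected.

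**Working it through.** **Inputs.** The documents give no QT value, heart rate, threshold or expected change, so there is no stated figure to reproduce. I assume QTc of 400-420 ms and a resting heart rate (HR) of 70-90 bpm at Baseline. HR is recorded at the same ECG, so the correction needs no new data.

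**Formulas.** Fridericia: QTcF = QT / (60/HR)^(1/3), so QT = QTcF × (60/HR)^(1/3). Bazett uses the exponent 1/2.

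**Step 1: rate change only.** Hold QTcF constant and change HR. Example at QTcF 400 ms, from 80 to 90 bpm: 400 × (60/80)^(1/3) = 363.4 ms and 400 × (60/90)^(1/3) = 349.4 ms, a fall of 14.0 ms with no true effect. Over the assumed range, the change in raw QT (ms, Fridericia) is:

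| QTcF (ms) | Baseline HR (bpm) | -10 bpm | -5 bpm | +5 bpm | +10 bpm |
|---|---|---|---|---|---|
| 400 | 70 | +20.0 | +9.5 | -8.6 | -16.5 |
| 400 | 80 | +16.5 | +7.9 | -7.3 | -14.0 |
| 400 | 90 | +14.0 | +6.7 | -6.2 | -12.1 |
| 420 | 70 | +21.0 | +10.0 | -9.1 | -17.4 |
| 420 | 80 | +17.4 | +8.3 | -7.6 | -14.7 |
| 420 | 90 | +14.7 | +7.1 | -6.6 | -12.7 |

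A 5 bpm change therefore moves raw QT by about 6-10 ms. A 10 bpm rise lowers it by about 12-17 ms, and a 10 bpm fall raises it by about 14-21 ms. With Bazett the corresponding figures are about 9-15, 17-25 and 20-31 ms.

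**Step 2: masking.** Let QTcF rise truly from 400 to 410 ms while HR goes from 80 to 90 bpm. Raw QT becomes 410 × (60/90)^(1/3) = 358.2 ms, which is 5.3 ms below the starting 363.4 ms before rounding. The true +10 ms appears as a fall. It is cancelled exactly at 80 × (410/400)^3 = 86.2 bpm.

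**Step 3: do separate summaries of QT and HR suffice?** Take two subjects, each starting at 80 bpm with QT 363.4 ms (QTcF 400) and each with an unchanged raw QT. One moves to 90 bpm: QTcF = 363.4 / (60/90)^(1/3) = 416.0 ms (+16.0). The other moves to 70 bpm: QTcF = 363.4 / (60/70)^(1/3) = 382.6 ms (-17.4). Mean HR and mean QT are both unchanged, yet neither subject's QTcF is. Group summaries of the two variables do not recover individual QTc or its change.

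**Step 4: size against precision.** SAP section 6 plans 10 to 15 subjects within a cohort. With an assumed SD of the paired change of 10-20 ms, the 95% half-width t(0.975, n-1) × SD/√n is 7.2-14.3 ms for n = 10 and 5.5-11.1 ms for n = 15. A mean shift of 10 bpm would thus produce an artefact of about the size of the sampling error or larger. A mean shift of 5 bpm would usually sit within it.

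**The case against.** The strongest case against is that little depends on this table, and most of that case is sound.

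- Protocol 1.2.1 says that prostacyclins do not affect heart rate. Cohorts 1 and 2 (25 of 40 subjects) must have had at least 90 days of Remodulin or inhaled prostacyclin before entry (Protocol 4.1), so a large drug-related rate change is least plausible there. Tachycardia in Protocol Table 9-1 is listed as an event of the disease, not of the drug. A reader might infer that heart rate will change because the drug is a vasodilator. The documents do not support that: a treatment effect on rate is possible but not established. The point does not need one, because ordinary visit-to-visit variation is enough. The five-minute semi-recumbent rest reduces that variation without removing it.
- A reader might also infer that the ECG results would be worthless as safety evidence. That goes too far. Heart rate is summarised alongside QT, both are listed per subject, each tracing is classed normal or abnormal, and abnormalities are assessed for clinical significance. Protocol Appendix 15.4 also has the investigator report clinically significant changes in diagnostic tests as adverse events.
- ECG is not among the primary safety assessments named in Protocol 3.3.2, and the SAP places it under other safety measures. With one scheduled post-baseline ECG, no timing relative to dose and no control group, even QTc gives only a coarse signal.
- The size depends on the formula, and the documents give no basis for preferring one. Unplanned analyses are permitted (Protocol 10.5, SAP section 1), so nothing is lost for good.

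These points limit the impact. They do not close the gap: Step 3 shows why the planned summaries cannot stand in for individual QTc, and a formula chosen after the data are seen is weaker than one fixed in advance.

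**Conclusion.** The concern holds in a limited form. As written, SAP 11.8.1 gives uncorrected QT by visit with no numeric change from Baseline, and this falls short of the protocol's stated aim of evaluating treatment-emergent ECG change. Raw QT would not be interpretable for repolarisation without correction. The artefact is about 6-10 ms for a 5 bpm change and about 12-17 ms for a 10 bpm rise (Fridericia), resting on the assumed QTc of 400-420 ms and heart rate of 70-90 bpm. A cohort mean is affected only through the average rate shift, for which the documents give no figure. Larger illustrations, such as a 20 bpm rise taking a QT of 380 ms at 70 bpm to about 349 ms at constant QTcF, are arithmetically correct but rest on a shift that nothing in the documents indicates. The impact is modest: one descriptive safety table, with partial protection from the listing and the investigator's assessment.

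**What to change.** In SAP 11.8.1, define a per-subject QTc from the QT and heart rate recorded at the same ECG, with the formula named in advance (for example Fridericia, with Bazett as a check). In Table 14.3.4.5, summarise QTc and its change from Baseline by cohort, and add change from Baseline for heart rate, PR, QRS and raw QT. Show QTc beside raw QT in Listing 16.2.8.4.

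The cost is one derived variable (two if the check formula is kept) and a few table rows, with no new visit, procedure or data collection. The downside is that the result depends somewhat on the formula. Reporting the second formula makes that dependence visible.
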